### 3.5.2. Laboratory Data

For the specific laboratory parameters listed in Table 2 below, the following endpoints will be evaluated using CaPS:

- Absolute value and change from baseline at week 2, week 4, week 6, and 1st Follow-up visit.
- Number of occurrences of these abnormalities defined as “Flag Level” or “Alert Level”
- Number of participants with these abnormalities defined as “Flag Level” or “Alert Level”

**Table 2. Clinical Laboratory Parameters of Interest in Study C3711005**

Parameter	Flag Level	Alert Level	Conventional Units
Fasting Serum Triglycerides	≥ 400	≥ 600	mg/dL
	--	≥ 800	mg/dL
Platelet Count	< 100,000	< 75,000	/mm 
Fasting Plasma Glucose	< 70	≤ 49	mg/dL

**Table 2. Clinical Laboratory Parameters of Interest in Study C3711005**

Parameter	Flag Level	Alert Level	Conventional Units
Alanine aminotransferase	≥ 140	> 270	mg/dL
	≥ 2x ULN	--	U/L
	> 3x ULN	--	U/L
	> 5x ULN	>8x ULN	U/L
Aspartate aminotransferase	≥ 2x ULN	--	U/L
	> 3x ULN	--	U/L
	> 5x ULN	>8x ULN	U/L
	≥ 2x ULN	--	U/L
Alkaline Phosphatase	> 3x ULN	--	U/L
	>5x ULN	--	U/L
	> ULN	--	U/L
Total Bilirubin	> 1.5x ULN	>3x ULN	mg/dL
Direct (Conjugated) Bilirubin	> ULN	--	mg/dL

\*All flag level changes are cumulative from baseline (defined as result closest prior to dosing at Visit 4 (Day 1); reflect either threshold for entry criteria into study or clinically significant thresholds

^All alert changes are cumulative from baseline (defined as result closest prior to dosing at Visit 4 (Day 1); values when noted during the study, by central laboratory necessitates rapid notification (via fax/e-mail) to site and Study Clinician, Pfizer Medical Monitor, and Global Clinical Lead, *in parallel*

ULN – upper limit of normal as determined by the central laboratory

Across all the laboratory-related analytes (for safety and pharmacodynamics/biomarker), inclusion of results when assessed at scheduled nominal visits meet the following criteria:-

1. Collection must be prior to AM dose of double-blinded study medication
2. Collection permitted to be *nonfasted for the following analytes and will be permitted to be grouped with fasted results* given that nonfasted state is not known to impact results

Chemistry panel	Hematology	Other	Urinalysis
Direct bilirubin	Hemoglobin	aPTT	pH
Indirect bilirubin	Hematocrit	PT	Protein
Urea Nitrogen	RBC	INR	Glucose
Creatinine	MCV	Urine-drug-testing	Ketones
Uric acid	MCH	Serology testing	Bilirubin
Calcium	MCHC	[hepatitis B, hepatitis C, HIV]	Urobilinogen
Total protein	WBC	Alpha-1-antitrypsin	Blood
Albumin	Neutrophils (abs)	Ceruloplasmin	Nitrite
Creatine kinase	Lymphocytes (abs)	β-hCG	Leukocyte esterase
Sodium	Monocytes (abs)	FSH	Microscopic UA
Potassium	Eosinophils (abs)		
Bicarbonate	Basophils (abs)		
Chloride	Platelets		
	Reticulocyte count%		
	Reticulocyte count		

3. **But**, the following analytes will only be included in summary outputs if collections are confirmed to be following an overnight fast of at least 8 hours as it is well known that fasting status impacts numerical results (**or** there is insufficient data regarding effect of meals on results)

Biomarkers	Lipid-related	Other Blood-related
% CDT	Total cholesterol	Prep B1.5 (plasma) and B2.5 (serum) related mechanistic/disease-related biomarkers
Plasma Glucose	HDL-C	
Plasma Insulin	Direct LDL-C	
Total Bile Acids	Triglycerides	
Plasma PCSK9	VLDL	
CK18-M30	Apolipoprotein A1	
CK18-M65	Apolipoprotein B Total	
ProC3	Apolipoprotein B 48	
ProC6	Apolipoprotein B 100	
	Apolipoprotein C3	
	Apolipoprotein E	

Note: Prep samples (ie Prep B1.5 (plasma) and B2.5 (serum)) if analyzed will consider the fasted collection and will be reported in a supplemental CSR.

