## **6.6. Safety Summaries and Analyses**

*All safety analyses will be performed on the safety population.*

*The safety data will be summarized in accordance with Pfizer Data Standards. All participants who receive study intervention (safety population) will be included in the safety analyses.*

*All safety data will be summarized descriptively through appropriate data tabulation, descriptive statistics, categorical summaries, and graphical presentations.*

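### SAP 3.5.2 removes scheduled safety laboratory results drawn after the morning dose, and non-fasted low glucose, from the Table 2 Flag/Alert summary counts; this can only lower those counts

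*SAP*

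**What the plan says.** SAP 3.5.2 defines the laboratory safety endpoints for the Table 2 parameters: values and changes by visit, the number of abnormal occurrences, and a participant count, "Number of participants with these abnormalities defined as" Flag or Alert level. Table 2 includes platelets (Flag below 100,000/mm³, Alert below 75,000/mm³), ALT and AST (Alert above 8 times ULN), bilirubin, triglycerides, and "Fasting Plasma Glucose" with low levels of below 70 mg/dL (Flag) and 49 mg/dL or less (Alert).

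Below Table 2, the same section sets inclusion rules: "Across all the laboratory-related analytes (for safety and pharmacodynamics/biomarker), inclusion of results when assessed at scheduled nominal visits meet the following criteria". There are three:

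- Criterion 1: "Collection must be prior to AM dose of double-blinded study medication".
- Criterion 2 accepts non-fasted samples for a list of analytes that includes platelets and direct bilirubin. It relaxes fasting only, not timing relative to the dose.
- Criterion 3: a second list, which includes triglycerides and "Plasma Glucose", "will only be included in summary outputs if collections are confirmed to be following an overnight fast of at least 8 hours".

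In the text available, ALT, AST, alkaline phosphatase and total bilirubin are on neither fasting list. Criterion 1 still covers them.

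Protocol 9.4.5 and SAP 6.6, which govern the safety analyses, set no pre-dose or fasting condition on laboratory results.

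**The concern.** A pre-dose, fasted sample is a sensible requirement for a pharmacodynamic endpoint such as fasting triglycerides, where timing and meals add noise to a mean. A count of participants who ever crossed a safety threshold is different: a platelet count below 75,000/mm³ is a safety finding whether the tube was filled before or after the morning tablets. Applying the pharmacodynamic filter to such a count discards usable abnormal results and gains nothing.

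The counts matter. Clinically significant abnormal laboratory tests are part of the secondary safety endpoint (Protocol 3). Platelet decrease is one of the two identified adverse reactions to ACCi (Protocol 2.2.1 and 2.3.1). SAP 7.1.1 sends the distribution of Table 2 boundary crossings to the Internal Review Committee (IRC). Low glucose is relevant because sulphonylureas and metformin are permitted (Protocol 6.5.1), and Protocol 2.3.1 reports that DGAT2i 300 mg BID can double metformin exposure.

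**Working it through.** The plan states no figure on this point, so there is none to reproduce. The check is a reading of the rules, followed by arithmetic for scale.

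**Step 1: follow individual scheduled results through the criteria.**

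| Result at a scheduled visit | Criterion 1 (pre-dose) | Fasting rule | Outcome as written |
|---|---|---|---|
| Platelets 70,000/mm³, pre-dose, non-fasted | passes | on the non-fasted-accepted list | counted |
| Platelets 70,000/mm³, post-dose | fails | not reached | not counted |
| ALT or AST above 8 times ULN, post-dose | fails | on neither list | not counted |
| Glucose 45 mg/dL, pre-dose, non-fasted | passes | fails criterion 3 | not in summary outputs |

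Nothing in 3.5.2, 6.2.2 or 6.6 exempts the Flag/Alert counts or says that they use all post-baseline results.

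**Step 2: compare with the protocol's treatment of mistimed draws.** For pharmacokinetic samples (Protocol 8.5) and exploratory biomarkers (Protocol 8.8), a scheduled pre-dose sample taken after the dose is recorded as a deviation, but the protocol allows that the result may still be usable. The SAP is therefore stricter with a safety platelet count than the protocol is with an exploratory biomarker.

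**Step 3: direction.** Let A be the participants with at least one result past a threshold among all results, and K the same among results that pass the criteria. Every kept result is also in the full set, so K is contained in A and |K| ≤ |A|. The same holds for occurrences. The filter can lower a count or leave it unchanged.

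**Step 4: scale.** Inputs: 18 participants per group and 5 groups in Part 1 (Protocol 4.1.1); scheduled on-treatment safety draws at Weeks 2, 4 and 6 (Protocol Table 2).

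- Weight of one participant: 1/18 = 5.6 percentage points of a group.
- Draws per group: 3 × 18 = 54. All groups: 5 × 54 = 270.

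The documents give no rate of post-dose draws. Let f be that rate, an assumption, with draws independent. Expected dropped draws per group are 54f. The chance that a group loses at least one draw is 1 − (1 − f)^54. If four alerts occur, each at one scheduled visit with no abnormal repeat, the chance that at least one is dropped is 1 − (1 − f)^4.

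| Assumed f | Dropped per group | Dropped overall (270f) | Group loses ≥1 draw | ≥1 of 4 single-visit alerts dropped |
|---|---|---|---|---|
| 0% | 0 | 0 | 0% | 0% |
| 1% | 0.5 | 2.7 | 42% | 4% |
| 2% | 1.1 | 5.4 | 66% | 8% |
| 5% | 2.7 | 13.5 | 94% | 19% |
| 10% | 5.4 | 27 | 99.7% | 34% |

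Most dropped draws would be normal. The last column bears on the counts, and it is an upper figure because abnormal results usually lead to repeats. Non-fasted glucose has its own unknown rate, which is not modelled here.

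**The case against.** The case for leaving the text alone is substantial, and much of it stands.

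- **Few draws are exposed.** Protocol Table 2 places treatment-phase collections before the morning dose, apart from post-dose PK samples, after a fast of at least 8 hours. Under Protocol 5.4.2 participants arrive unfed and undosed. Only deviations are affected.
- **Repeats escape the rule.** It governs scheduled visits. Protocol 8.2.8.2 calls for an unplanned visit with a hematology panel when platelets fall below LLN, and Protocol 8.2.5 asks for clinically significant abnormal tests to be repeated. A persistent abnormality can be counted through its repeat, although 3.5.2 does not state that unplanned results feed the counts.
- **Detection does not depend on the counts.** Alert values trigger rapid notification (SAP Table 2 footnote). Platelets below 75,000/mm³ and triglycerides of 800 mg/dL or more are adverse events of special interest (Protocol 8.3.6). The IRC also receives listings (SAP 7.1.1), and SAP 6.6.4.1 plots every participant with a post-Day 1 platelet count below 100,000/mm³, unplanned results included. A reader might infer that true alerts would go unnoticed; the documents do not support that.
- **The counts are not the leading safety display.** Protocol 9.4.5 and SAP 6.6.1 give that place to treatment-emergent adverse events.
- **SAP 6.6 is not contradicted.** "All participants who receive study intervention (safety population) will be included in the safety analyses" concerns which participants enter, not which samples. A reader might see a conflict there, but dropping one draw does not drop the participant.
- **No bias between arms is shown.** Dosing is double-blind and double-dummy, and nothing suggests that draw timing differs by arm. Lower absolute counts are supported; a distorted comparison with placebo is not.
- **Glucose is labelled fasting in Table 2.** Requiring a confirmed fast applies the stated definition. Counting non-fasted lows within that row would change the parameter.
- **Intent may be narrower.** The lead-in sentence is loosely worded and may be meant for by-visit summaries. The endpoints are produced with sponsor tools and standards that are not part of these documents.

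The last point does not rescue the text. The SAP nowhere limits the criteria to by-visit outputs. It is also unclear whether such outputs exist for safety laboratory data: 6.2.2 applies visit windows to them, while Appendix 2.1 says that no summaries by visit window are planned. A programmer following 3.5.2 literally would remove the values.

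**Conclusion.** The point holds in a limited form. As written, SAP 3.5.2 excludes a scheduled safety result drawn after the morning dose from the Table 2 Flag/Alert counts, and excludes a non-fasted low glucose from summary outputs. Both exclusions act in one direction, towards fewer reported abnormalities. They touch only draws that deviate from the schedule.

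The size cannot be determined from the documents. It is zero if every draw complies. At assumed post-dose rates of 1% to 10%, the chance of losing at least one of four single-visit alerts runs from 4% to 34%, assuming independent draws and no abnormal repeat. One lost participant moves a group's percentage by 5.6 points. The low-glucose part is the weaker half, since it asks for a modest addition to what Table 2 defines.

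**What to change.** Revise the paragraph below Table 2 in SAP 3.5.2:

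1. Confine criterion 1 to the pharmacodynamic and biomarker analyses and, if wanted, to by-visit summaries of laboratory values.
2. State that the Table 2 Flag and Alert counts, for occurrences and participants, use every post-baseline result, scheduled or unplanned, whatever its timing relative to the dose. For unplanned results this is a clarification, since the present rule does not exclude them.
3. Keep the confirmed-fast condition for triglycerides and high glucose.
4. Report non-fasted glucose values below the low thresholds in a separate, labelled row, so that the fasting definition in Table 2 stays intact.
5. Say how non-fasted ALT, AST, alkaline phosphatase and total bilirubin are handled, if the full SAP lists do not already do so.

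The cost is one SAP paragraph and a small programming change, with no new data and no change to study conduct. The downside is that some abnormality counts may rise slightly.

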### 3.5.3. Standard Safety Other than AEs

#### 3.5.3.1. Vital Signs of Special Clinical Concerns

Individual participants' vital signs outlined in Table 3 of special clinical concern, which align with the Pfizer standard criteria, will be summarized by treatment, as part of standard safety-related outputs.

**Table 3 Vital Signs to be Monitored**

Parameter	Flag Level*	Conventional Units
Systolic Blood Pressure (seated)	< 90	mm Hg
	≥ 30 change from baseline	mm Hg
Diastolic Blood Pressure (seated)	< 50	mm Hg
	≥ 20 change from baseline	mm Hg
Pulse rate (seated)	< 40	Bpm
	> 120	Bpm

\*All flag level changes are cumulative from baseline (defined as result closest prior to dosing at Visit 4 (Day 1))  
bpm – beats per minute

In addition Pfizer standard criteria for reporting of cardiac conduction intervals will be summarized by treatment.

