    - Those on statins will be permitted based on review of the total daily dose, refer to [Section 6.5.2](#).
7. At PreQ **or** SCR, those with severe hypertension defined as seated systolic BP  $\geq 180$  mmHg and diastolic BP  $\geq 105$  mm Hg with a single repeat permitted, if needed, to assess eligibility **at each** of these 2 visits; **and/or** managed with >3 agents to control BP within 12 weeks prior to SCR (refer to [Section 6.5.3](#) for acceptable medications):
  - BP must be assessed using a blood pressure cuff size available at individual sites and compatible with the arm circumference of the participant, refer to [Section 8.2.4](#);
  - Participants with seated BP  $\geq 160/100$  mmHg at PreQ **or** SCR to use the Run-In period to revise/adjust medications to improve BP control;
    - In those with hypertension, BP must be well-controlled in order to progress with randomization, refer to [Section 5.3](#).
8. Cardiovascular event within 12 months prior to PreQ:
  - A history of myocardial infarction, stroke, transient ischemic attack or revascularization procedure to prevent any of these events;
  - A history of congestive heart failure (NYHA class III or IV) or unstable angina.
9. Recent (within 5 years of PreQ) systemically administered treatments for malignancy including (but not limited to) the use of chemotherapy, radiotherapy, **or** immunotherapy.
  - **Or** any other active malignancy (within 3 years of PreQ), except for adequately treated basal cell or squamous cell skin cancer, or carcinoma *in situ*.
10. Other medical or psychiatric condition including recent (within the past year) or active suicidal ideation/behavior or laboratory abnormality that may increase the risk of study participation or, in the investigator's judgment, make the participant inappropriate for the study.

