### 5.3. Randomization Criteria

A computer-generated randomization code using the method of random permuted blocks will be utilized to randomize participants equally balanced across the study interventions on Day 1/Visit 4 ***prior*** to the first dose of the double-blind, double-dummy study intervention provided participants satisfy ***all*** the following criteria:

1. Eligibility criteria outlined in [Section 5.1](#) and [Section 5.2](#);
2. A negative urine drug test for illicit drugs for sample collected at Baseline/Visit 3, as reported by Sponsor-identified central laboratory (with repeat assessment ***not*** permitted for this visit);
3. Fasting ( $\geq 8$  hours overnight, with water permitted) serum triglyceride result of  $\leq 400$  mg/dL (4.5 mmol/L), for sample collected at Baseline/Visit 3, as reported by Sponsor-identified central laboratory;
  - A single repeat assessment permitted using Sponsor-identified central laboratory, though results of this repeat, when done, must be available ahead of randomization;
4. Fasting ( $\geq 8$  hours overnight, with water permitted) plasma glucose result of  $\leq 270$  mg/dL (15 mmol/L), for sample collected at Baseline/Visit 3, as reported by Sponsor-identified central laboratory;
  - A single repeat assessment permitted using Sponsor-identified central laboratory, though results of this repeat, when done, must be available ahead of randomization, refer to [Appendix 10.10](#).
5. In females, a negative ***serum*** pregnancy test result for sample collected at Baseline/Visit 3, as reported by Sponsor-identified central laboratory;
  - ***Plus***, in females of childbearing potential, ***urine*** pregnancy test on Day 1/Visit 4, as reported on-site using supplies offered by Sponsor-identified central laboratory, must be negative for pregnancy, refer to [Section 8.2.6](#);
6. In those with hypertension, BP controlled via adjustment of concomitant medications for BP control during the Run-In period with seated BP on Day 1/Visit 4 of  $<160/100$  mmHg;
7. Compliance of  $\geq 90\%$  and  $\leq 110\%$  with ***doses*** of single-blind placebo administered (based on tablet count) from Baseline/Visit 3 to 1 day before Day 1/Visit 4, inclusive, refer to [Section 6.4](#);

8. Total score of <8 on the AUDIT questionnaire, as assessed on Day 1/Visit 4;

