##### **9.4.5.1. Vital Signs Analyses**

Changes from baseline in systolic blood pressure, diastolic blood pressure and pulse rate will be summarized by treatment and time. The number (%) of participants with maximum increases from baseline will be tabulated by treatment as defined in the SAP. Numbers and percentages of participants meeting the categorical criteria will be provided and individual values listed in the study report. No formal inferential statistics will be applied to the vital signs data.

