Individual vital signs (blood pressure and pulse rate) via a listing of the raw data as well as values meeting the criteria outlined in Table 3 of this SAP will be provided.

No formal statistical analyses (eg MMRM) will be performed on safety data, for purposes of IRC review of unblinded safety data.

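### SAP Table 3 has no upper blood-pressure limit, so the by-arm counts miss a crossing of 160/100 or 180/105 when the rise is under 30/20 mm Hg

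*SAP*

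**What the plan says.** **Categories.** SAP 3.5.3.1 states that individual "vital signs outlined in Table 3 of special clinical concern, which align with the Pfizer standard criteria, will be summarized by treatment". Table 3 flags:

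- systolic pressure below 90, or "≥ 30 change from baseline";
- diastolic pressure below 50, or "≥ 20 change from baseline";
- pulse below 40 or above 120.

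The footnote fixes the reference point: "All flag level changes are cumulative from baseline (defined as result closest prior to dosing at Visit 4 (Day 1".

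**Protocol levels.** Exclusion criterion 7 (Protocol 5.2) removes "those with severe hypertension defined as seated systolic BP" at or above 180 and diastolic at or above 105. The same criterion sends participants at or above 160/100 to medication adjustment during the run-in. For participants with hypertension, randomization criterion 6 (Protocol 5.3) requires "BP controlled via adjustment of concomitant medications for BP control during the Run-In period with seated BP on Day 1/Visit 4 of" below 160/100.

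**Reporting.** Protocol 9.4.5.1 says: "The number (%) of participants with maximum increases from baseline will be tabulated by treatment as defined in the SAP". SAP 6.6.2 repeats this and refers to SAP 5.2.3 for the definition, but SAP 5.2.3 offers only generic counts and percentages, with no cut-points. For the IRC, SAP 7.1.1 provides a raw listing of blood pressure and pulse, and "values meeting the criteria outlined in Table 3 of this SAP will be provided".

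**The concern.** The proportion of participants with clinically significant abnormal vital signs is part of the secondary safety endpoint (Protocol 3; SAP 2.1 and 3.2.2). Table 3 is the only set of blood-pressure categories with stated cut-points, and no row in it is triggered by a high level as such. A participant who starts fairly high and rises by less than 30/20 can pass a level that the protocol itself treats as important without entering any category.

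The table is also out of step with its neighbours. Pulse has a high limit. The Table 2 footnote says that laboratory flags reflect entry thresholds or clinically significant ones, and the triglyceride flag of 400 mg/dL matches the entry limit. The blood-pressure entry levels were not carried over in the same way.

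At stake is whether a reader can compare arms on the number of participants who became markedly hypertensive on treatment. Mean changes and listings do not give that number directly.

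**Working it through.** The plan states no figure to reproduce, so the check applies Table 3 to possible readings.

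**Inputs.** Change thresholds 30 (systolic) and 20 (diastolic), from SAP Table 3. Highest Day 1 value 159/99, from Protocol 5.3 criterion 6 (participants with hypertension). Levels 180/105 and 160/100, from Protocol 5.2 and 5.3. Change is observed minus baseline (SAP 3.4), so rises count.

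**Step 1: which baselines can cross unflagged.** In whole mm Hg, a participant reaches level L unflagged by a change row with threshold T only if L − baseline ≤ T − 1, that is, baseline ≥ L − (T − 1).

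| Level | Calculation | Day 1 values that can cross unflagged |
|---|---|---|
| Systolic 180 | 180 − 29 = 151 | 151–159 |
| Diastolic 105 | 105 − 19 = 86 | 86–99 |
| Systolic 160 | 160 − 29 = 131 | 131–159 |
| Diastolic 100 | 100 − 19 = 81 | 81–99 |

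The other component must also stay under its own threshold.

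**Step 2: highest unflagged reading.** 159 + 29 = 188 and 99 + 19 = 118. So 159/99 to 188/118 meets no row, and neither does 155/95 to 182/108 (+27/+13). The gap is bounded: 150/90 to 180/106 is flagged, because the systolic rise is 30.

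**Step 3: how often, under assumptions.** The documents give no blood-pressure distribution. Assume:

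- Day 1 mean 130–135/80–83, SD 13/9, truncated below 160/100;
- SD of change 11–12/7–8;
- systolic–diastolic correlation 0.6, both at Day 1 and for change;
- one on-study reading per participant;
- an illustrative drug effect of +10 to +15 / +6 to +8.

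The unflagged share is P(level reached and no Table 3 row met) ÷ P(level reached). The expected unflagged number per arm is 18 × P(level reached) × share.

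| Level reached | Unflagged share | Expected unflagged per 18-person arm (lowest and highest scenario) |
|---|---|---|
| Systolic ≥180 **and** diastolic ≥105 | about 12–28% | 18 × 0.0024 × 0.23 = 0.01 to 18 × 0.0112 × 0.21 = 0.04 |
| Systolic ≥180 **or** diastolic ≥105 | about 44–70% | 18 × 0.041 × 0.67 = 0.5 to 18 × 0.098 × 0.57 = 1.0 |
| Systolic ≥160 **or** diastolic ≥100 | about 62–84% | 18 × 0.167 × 0.80 = 2.4 to 18 × 0.333 × 0.74 = 4.4 |

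With no drug effect, the last row is about 18 × 0.054 × 0.94 = 0.9 to 18 × 0.100 × 0.92 = 1.7 per arm. These figures show the shape of the gap and do not forecast this trial.

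**The case against.** **Falls are not shown to be pooled with rises.** Table 3 does not write a direction, so a reader might infer that a 30 mm Hg fall is counted together with a 30 mm Hg rise. The documents do not support this. SAP 3.4 defines change as observed minus baseline, so a fall of 30 is −30 and does not meet the row. SAP 6.6.2 likewise speaks of increases. A clearer label is all that is needed.

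**The participants are not hidden.** A reader might infer that a reading of 188/118 would go unseen. It would not. The IRC receives the raw listing unblinded, at about 30 and 60 of 90 randomized in Part 1, which is short enough to read through. The report lists individual values and summarizes mean changes. A value judged clinically significant meets the adverse-event definition and is counted by arm (Protocol 10.3.1; SAP 6.6.1). Changes in blood-pressure medication are summarized by treatment (SAP 3.5.3.3 and 6.5.4). This stands and limits the concern. However, these routes depend on investigator judgement, medication changes or reading line by line, and none gives a by-arm count at a fixed level.

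**A signal is not expected.** Protocol 2.2.1 reports no clinically significant adverse blood-pressure effects for either agent or the combination. The drug effect assumed above therefore has no support in the documents. This also stands.

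**Table 3 follows the sponsor's standard.** Eligibility levels need not be reporting levels, so the choice of cut-point is partly preference. But the statement that Table 3 aligns with the standard also means that no further blood-pressure category can be assumed.

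**Conclusion.** The point holds as a modest gap in reporting. Table 3 has no upper absolute limit for blood pressure, and the tabulation of maximum increases has no cut-points, so the by-arm categories do not capture crossings of a high level. The bounds in Steps 1 and 2 rest only on Table 3 and the Day 1 limit.

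A reader might go further and conclude that about half or more of severe hypertension would be missed. That is not supported. Exclusion criterion 7 requires systolic ≥180 and diastolic ≥105 together. On that definition the unflagged share is about 12–28%, and the expected number is below 0.05 per 18-person arm. The share of about 44–70% applies only when either component suffices. All of these shares depend on assumed distributions and an assumed drug effect. The larger gap is at 160/100, where one to several participants per arm could cross unflagged under the same assumptions.

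No endpoint estimate changes and no data are lost. The change is worth making because it is specific and nearly free.

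**What to change.** In SAP Table 3:

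- Add descriptive rows for systolic ≥160 and ≥180, diastolic ≥100 and ≥105, and the joint definition (systolic ≥180 and diastolic ≥105). These levels already stand in Protocol 5.2 and 5.3.
- Count them by arm among participants who were below the level on Day 1.
- Label the 30 and 20 mm Hg change rows as increases, in line with SAP 3.4 and 6.6.2. If falls are also of interest, give them a separate decrease row.
- Point the maximum-increase tabulation in SAP 6.6.2 to Table 3 instead of 5.2.3, and use the same table in the IRC package (SAP 7.1.1).

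With these rows, 159/99 to 188/118 is counted at every level.

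The cost is a short SAP edit and a few extra table rows, with small counts per arm that should be read descriptively. No new data are needed. This is a counting rule only and changes nothing in patient management.
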